##### Secondary outcomes:

- Severity of UTI symptoms based on validated questionnaire, with the expectation of a decrease in UTI symptom severity while on Hiprex.

- Duration of intervals between UTI episodes considering that Hiprex may lessen the frequency of oral antibiotics usage to treat symptomatic UTI episodes.
- Reduction in number of hospital admission and IV antibiotics (PICC line) for urosepsis and/or pyelonephritis compared to the pre-Hiprex situation.
- Frequency and severity of adverse effects related to Hiprex, requiring treatment interruption, dose adjustment, or discontinuation.
- Evaluation of possible gradual increase in bacterial resistance to formaldehyde by testing its concentration in the urine at each visit, urine acidity, and ability to kill established bacterial strains (UTI89, CFT073)

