#### **4. Study Procedures:**

##### Initial visit:

Patients will be consented for the study. Patients will also be advised to return to clinic sooner than scheduled follow-up visits if they start to develop symptoms of a UTI (pain with urination, cloudy or bloody urine, etc.) or experience any side-effects that may be attributed to Hiprex. Patients who have previously been on a methenamine-containing substance will be asked about their medication history, including the length of time on the medication, the dosage and any changes to dosage, and side-effects experienced while taking the medication. Patients will be prescribed Hiprex 1 g PO BID for 3 months with 4 refills (total of 1 year). Urine samples will be obtained from patients prior to their first dose intake. Those will be mid-stream urine sample, with a collection volume around 30 ml.

Those with negative cultures (after 48-72 hours) will begin their first dose of Hiprex. Those with positive cultures will be treated with a course of culture-based antibiotics and will start their first dose of Hiprex when they can produce negative urine cultures. Using a formaldehyde assay, the concentration of formaldehyde in the urine samples with negative cultures of each patient will be measured. A pH meter will be used to determine the acidity of the urine samples.

In the lab of [name], the following studies will be performed on de-identified urine samples:

**Sample preparation:** The urine samples will be frozen at  $-80^{\circ}\text{C}$ . Upon thawing for assay, the urine will be adjusted to pH 8.0 by adding 50 mM HEPES buffer and checked with pH paper in order to prevent methenamine breakdown, which occurs rapidly at  $\text{pH} < 6$ . The sample will be centrifuged to remove particulates and the soluble portion filter sterilized.

**Formaldehyde assay:** A variety of formaldehyde assays are available (summarized in X1). We will use a glutathione-dependent formaldehyde dehydrogenase (FDH)-based assay (X2). The urine sample will be diluted 10- to 1000-fold and placed in a microtiter dish well. The reaction will also contain 50 mM HEPES buffer (pH 8), 0.5 mM reduced glutathione, 0.5 mM NAD, and FDH (the FrmA protein) purified from *Escherichia coli*. The increase in NADH is proportional to the amount of formaldehyde. The mM extinction coefficient for NADH is 6.27. To ensure the linearity of the reaction, a known amount of formaldehyde will be added to this reaction in a separate reaction.

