#### Follow-up:

Patients will be asked to return to clinic for 3 follow-up visits at: 3 months (V1), 6 months (V2), and 12 months (V3) after starting Hiprex. This research visit timing corresponds to standard-of-care clinic visits include those at 3 months, 6 months, and 12 months.

At each of these visits, patients will be asked to withhold their first dose of Hiprex until they arrive to clinic. Urine samples will be collected at baseline, then 1 hours after the dose intake. These samples will be tested according to the same protocol in the lab of [name]. In addition, patients will be administered a UTI Symptom Assessment (UTISA) questionnaire and queried about any UTI symptoms and Hiprex-associated symptoms since their last visit. If the concentration of methenamine/formaldehyde in the urine sample is found to be inadequate for bacteriostatic or bactericidal activity, the dosage might be increased to 1.5 PO BID, and/or diet-adjustment might be considered to decrease urine pH if found to be not sufficiently acidic. For patients unable to reach appropriate low pH urinary levels after the above modifications, they will be removed from the study and will not continue with the longitudinal portion.

Data:

The dataset will be extracted from EPIC and will include demographic data (age, gender, race, height, weight) as well as culture data from prior urinary tract infections, comorbid conditions (i.e. diabetes, renal insufficiency, etc.), hormonal status, methenamine usage history, and urological history (including possible surgical interventions). See Excel document.

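### The formaldehyde-resistance endpoint measures the urine, not the patient's bacteria, so it cannot show that resistance did or did not develop

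*Combined protocol and SAP*

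**What the plan says.** Section 3, Secondary outcomes, ends with an endpoint whose stated aim is "Evaluation of possible gradual increase in bacterial resistance to formaldehyde by testing its concentration in the urine at each visit". The same bullet adds two further readouts: "urine acidity, and ability to kill established bacterial strains (UTI89, CFT073".

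Section 4, Initial visit, describes how research urine is handled: it is frozen, thawed and brought to pH 8.0, and then "The sample will be centrifuged to remove particulates and the soluble portion filter sterilized". The laboratory methods that follow are a formaldehyde assay and a methenamine assay. For the follow-up visits, Section 4 says: "These samples will be tested according to the same protocol in the lab of [name"]. The culture information listed for the dataset in Section 4 is "culture data from prior urinary tract infections".

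No section describes how the killing assay is done, provides for keeping the patient's isolates, tests their susceptibility to formaldehyde, or says how the three readouts would be combined into a finding on resistance. Section 14 gives an enrolment goal of 100 for a pilot and attaches no test or threshold to this endpoint.

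**The concern.** The label and the measurements do not match. Acquired resistance would appear as a shift in the formaldehyde concentration needed to inhibit the bacteria that colonise or infect a given woman. The plan measures how much formaldehyde her urine contains, how acid it is, and what it does to two standard strains. None of these depends on the susceptibility of her own flora.

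The report could therefore make a statement about resistance that the data cannot carry. Flat results over a year of exposure could be taken as reassurance, and declining ones as a warning. Either statement could be carried into the randomised trial that Sections 3 and 14 say this pilot is meant to inform.

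**Working it through.** The plan states no power, alpha, effect size or threshold for this endpoint, so there is no figure to reproduce. The check is one of logic, with a numerical illustration.

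**Step 1. What each readout depends on.**

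| Readout (Section 3) | Depends on | Depends on the patient's bacteria? |
|---|---|---|
| Urinary formaldehyde | dose, time since dose, pH, dilution | no |
| Urine acidity | diet, physiology, drug | no |
| Killing of UTI89 and CFT073 | the above, and the fixed susceptibility of those strains | no |

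Write killing as a function of urine U and test-strain susceptibility S. If S is the same at every visit, a change between visits comes from U alone. The susceptibility of the patient's isolate does not enter the function. The one assumption is that the two strains are kept as stable stocks and not passaged in patient urine. The protocol does not describe their handling, but calls them established and names them.

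**Step 2. Inputs for the illustration.** From Section 2: 25 µg/mL as the bacteriostatic level, and methenamine hydrolysis 20 times faster at pH 5.0 than at pH 6.0. Assumed: starting urinary formaldehyde of 30, 50 or 100 µg/mL; formaldehyde proportional to the hydrolysis rate; log-linear interpolation between the two pH values; reference-strain susceptibility equal to 25 µg/mL. Inhibition stands in for killing.

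The interpolation can be compared with another pair of figures in Section 2, 0.6 mg/mL methenamine at pH 5.7 and 1 mg/mL at pH 5.85. These imply a ratio of 1/0.6 = 1.67; the formula gives 20^0.15 = 1.57, which is similar.

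**Step 3. Real resistance leaves the endpoint unchanged.** With urine at 50 µg/mL:

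| Patient isolate needs (µg/mL) | Patient isolate inhibited | Reference strain (25) inhibited |
|---|---|---|
| 25 | yes | yes |
| 50 | yes | yes |
| 100 | no | yes |
| 200 | no | yes |

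**Step 4. A change in urine moves the endpoint with no change in bacteria.** Relative formaldehyde = 20^(−ΔpH), which is 0.638, 0.407 and 0.224 for pH rises of 0.15, 0.3 and 0.5.

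| Start (µg/mL) | ΔpH 0.15 | ΔpH 0.3 | ΔpH 0.5 |
|---|---|---|---|
| 30 | 19.1 | 12.2 | 6.7 |
| 50 | 31.9 | 20.4 | 11.2 |
| 100 | 63.8 | 40.7 | 22.4 |

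Values below 25 would lose inhibition of the reference strain: all three pH rises from a start of 30, two of three from 50, and one of three from 100.

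**Step 5. Other sources of drift.** Section 3, Part 2, and Section 4, Follow-up, allow dose or diet to change in response to these same measurements. A trend across visits therefore also contains the response to earlier results.

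**The case against.** The strongest case on the other side is that this is the last of five secondary outcomes in a single-arm pilot, with no test or decision attached. Formaldehyde and acidity are recorded beside the killing result, Section 3, Part 2, reports levels as a ratio to creatinine and collects compliance, and at follow-up visits the first dose is withheld until clinic, with urine taken before it and 1 hour after. An analyst could trace lost killing to the urine. That is right, and it limits the damage. It does not rescue the endpoint, because once the change has been attributed to the urine, no resistance signal remains.

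A reader might infer four stronger things, and the documents support none of them.

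- *That low formaldehyde would be reported as resistance.* The wording makes this possible, but no decision rule says so, and the companion measurements allow the correct attribution.
- *That follow-up formaldehyde is measured only in culture-negative urine.* The phrase "the concentration of formaldehyde in the urine samples with negative cultures of each patient will be measured" stands under Initial visit, in the sequence that precedes the start of Hiprex. The later reference to the same protocol in the laboratory most naturally means the bench methods, and Section 3, Part 2, assays follow-up urine with no culture condition.
- *That the link between formaldehyde and breakthrough UTI cannot be studied.* Formaldehyde, methenamine and pH are measured at 3, 6 and 12 months and UTIs are counted over the year, so exposure can be related to UTIs, if less precisely than with urine taken at the episode.
- *That a definite number of informative isolates is being lost.* The documents give no UTI rate on treatment, and the primary outcome also counts treated UTI-like episodes without requiring a positive culture, so episodes cannot be equated with isolates.

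**Conclusion.** The endpoint is wrong as written. It cannot register acquired formaldehyde resistance in the patient's own bacteria at any sample size, because nothing it measures depends on their susceptibility. This rests on the reference strains being held constant, which is an inference from how they are described, and on the absence of any isolate testing in the documents. The figures in the illustration rest on assumed concentrations and an interpolated pH effect; the conclusion does not.

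The consequence is limited to what may be concluded from this one secondary outcome. The primary outcome and the other secondary outcomes are untouched, and the measurements remain useful as a description of urinary antibacterial activity.

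**What to change.** Restate the outcome in Section 3 as *urinary bactericidal activity against reference strains (UTI89, CFT073) over time*, and delete the reference to bacterial resistance. State that it will be interpreted alongside formaldehyde, pH and creatinine from the same sample, with any dose or diet change since the previous visit shown. This is a wording change at no cost.

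Add a short description of the killing assay to Section 4, including whether it uses native urine or the sample adjusted to pH 8.0, since that decides whether acidity can influence the result. This is also a matter of text only.

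Only if the resistance question is kept: save isolates already grown in culture at entry and at breakthrough UTIs, and compare the formaldehyde MIC within patient and within species under standard conditions. This is optional extra bench work and storage. It would be informative only in women with at least two isolates, and for women already taking methenamine at entry the first isolate is not a pre-exposure baseline; the plan should say both.

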#### Recruitment:

All patients will be recruited from the urology practice of the PI (WCB3 4th floor).

As part of a pilot study, we plan on enrolling 100 patients over 18 months to gather sufficient data to power a more extensive randomized control trial later on, using either a placebo or a competitive low-dose antibiotic, such as Macrobid or Septra, based on the efficacy of Hiprex given at the proper dosing and in the right urinary pH milieu in this small cohort of RUTI women. The PI is raising the enrollment goal due to COVID being tentatively over and the team is able to recruit more subjects due to this.

#### **4. Study Procedures:**

##### Initial visit:

Patients will be consented for the study. Patients will also be advised to return to clinic sooner than scheduled follow-up visits if they start to develop symptoms of a UTI (pain with urination, cloudy or bloody urine, etc.) or experience any side-effects that may be attributed to Hiprex. Patients who have previously been on a methenamine-containing substance will be asked about their medication history, including the length of time on the medication, the dosage and any changes to dosage, and side-effects experienced while taking the medication. Patients will be prescribed Hiprex 1 g PO BID for 3 months with 4 refills (total of 1 year). Urine samples will be obtained from patients prior to their first dose intake. Those will be mid-stream urine sample, with a collection volume around 30 ml.

Those with negative cultures (after 48-72 hours) will begin their first dose of Hiprex. Those with positive cultures will be treated with a course of culture-based antibiotics and will start their first dose of Hiprex when they can produce negative urine cultures. Using a formaldehyde assay, the concentration of formaldehyde in the urine samples with negative cultures of each patient will be measured. A pH meter will be used to determine the acidity of the urine samples.

In the lab of [name], the following studies will be performed on de-identified urine samples:

**Sample preparation:** The urine samples will be frozen at  $-80^{\circ}\text{C}$ . Upon thawing for assay, the urine will be adjusted to pH 8.0 by adding 50 mM HEPES buffer and checked with pH paper in order to prevent methenamine breakdown, which occurs rapidly at  $\text{pH} < 6$ . The sample will be centrifuged to remove particulates and the soluble portion filter sterilized.

**Formaldehyde assay:** A variety of formaldehyde assays are available (summarized in X1). We will use a glutathione-dependent formaldehyde dehydrogenase (FDH)-based assay (X2). The urine sample will be diluted 10- to 1000-fold and placed in a microtiter dish well. The reaction will also contain 50 mM HEPES buffer (pH 8), 0.5 mM reduced glutathione, 0.5 mM NAD, and FDH (the FrmA protein) purified from *Escherichia coli*. The increase in NADH is proportional to the amount of formaldehyde. The mM extinction coefficient for NADH is 6.27. To ensure the linearity of the reaction, a known amount of formaldehyde will be added to this reaction in a separate reaction.

**Methenamine assay:** Methenamine breaks down to formaldehyde at acidic pHs (i.e., less than pH6). Standard assays for methenamine involve conversion of methenamine to formaldehyde. This becomes a problem when methenamine and formaldehyde are present together. To prevent this problem, we brought the pH of the urine sample to 8.0, which prevents methenamine degradation. To measure methenamine, the sample will be treated with acid (0.25 N HCl at  $60^{\circ}\text{C}$  for 10 minutes), which will completely convert the methenamine to formaldehyde. This solution will be neutralized, brought to pH 8.0, and assayed for formaldehyde as described above. The assay measures the sum of methenamine and formaldehyde, and the methenamine concentration is obtained by subtracting the formaldehyde from the first assay.

#### Follow-up:

Patients will be asked to return to clinic for 3 follow-up visits at: 3 months (V1), 6 months (V2), and 12 months (V3) after starting Hiprex. This research visit timing corresponds to standard-of-care clinic visits include those at 3 months, 6 months, and 12 months.

At each of these visits, patients will be asked to withhold their first dose of Hiprex until they arrive to clinic. Urine samples will be collected at baseline, then 1 hours after the dose intake. These samples will be tested according to the same protocol in the lab of [name]. In addition, patients will be administered a UTI Symptom Assessment (UTISA) questionnaire and queried about any UTI symptoms and Hiprex-associated symptoms since their last visit. If the concentration of methenamine/formaldehyde in the urine sample is found to be inadequate for bacteriostatic or bactericidal activity, the dosage might be increased to 1.5 PO BID, and/or diet-adjustment might be considered to decrease urine pH if found to be not sufficiently acidic. For patients unable to reach appropriate low pH urinary levels after the above modifications, they will be removed from the study and will not continue with the longitudinal portion.

Data:

The dataset will be extracted from EPIC and will include demographic data (age, gender, race, height, weight) as well as culture data from prior urinary tract infections, comorbid conditions (i.e. diabetes, renal insufficiency, etc.), hormonal status, methenamine usage history, and urological history (including possible surgical interventions). See Excel document.

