**Hiprex (methenamine hippurate) is one of the most widely prescribed antiseptics for the prophylaxis of RUTIs**[cit]. Earliest recorded usage of methenamine as a urinary antiseptic was described in 1899. Methenamine is hydrolyzed to ammonia and formaldehyde, which is bacteriostatic or bactericidal depending on its concentration. The rate of this hydrolysis was found to be greater in solutions with lower pHs, achieving formaldehyde concentrations of clinical use at prescription dosage when the pH was less than 6.0. Although the urine pH range varies from 5 to 8, a recent study from our group in post-menopausal women identified an average urine pH around 6.0 with daily variability in several patients, possibly related to diet intake. Furthermore, as methenamine is hydrolyzed, the production of ammonia alkalinizes the solution, slowing down the reaction. Thus, in 1961, in order to increase efficacy, its formulation with adding hippurate, which increases the acidity of urine, as Hiprex, was developed.

**A literature review on the metabolism and urinary excretion of methenamine produced sparse results.** Studies by Gollamudi and Strom detailed the use of silica cartridges to determine the concentration of methenamine and formaldehyde in a solution and test this new method on human urine after administration of Hiprex to subjects. However, this work has limitations, since only 11 participants were tested and the urine samples were only taken after the first dose of Hiprex rather than after several days or months of Hiprex intake. Strom also analyzed the kinetics of methenamine, finding that a methenamine concentration of 750 µg/mL at pH 6.0 could produce bactericidal concentrations of formaldehyde after 3 hr and that the hydrolysis of methenamine occurred 20 times faster at a pH of 5.0 versus 6.0^14. Another study determined that the concentration of formaldehyde in urine adequate to produce a bacteriostatic effect (25 µg/mL) could be attained by adding 0.6 mg/mL of methenamine to urine at a pH ≤ 5.7 or 1 mg/mL at pH ≤ 5.85. Because the two latter experiments produced their results *ex vivo*, the rate of excretion of methenamine into the urine and the proof of its metabolism of conversion to formaldehyde in a patient's urine after an oral intake of 1 gm twice a day as currently recommended remains untested.

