### 3. Concise Summary of Project:

#### Study Design:

[figure not shown]
There will be two parts to this project. Part 1 will be a prospective assessment of the urinary effects of Hiprex in women with RUTIs, such as acidity and concentration of formaldehyde, to determine the best oral concentration to inhibit bacterial growth in urine for each enrolled patient. Part 2 will be a long-term assessment of Hiprex on RUTI evolution in women with a longstanding history of RUTIs, with Hiprex taken at a proper dosing (as established in Part 1) and with regular urine checks at subsequent visits up to one year of follow-up.

Part 1: Women between age 50 and 85 presenting to the outpatient UTSW Urology clinic who are currently taking Hiprex (or any methenamine-containing product) or are willing to be started on Hiprex and do not meet exclusion criteria (see below) will be invited to participate in the study. During their first study visit (V1), they will be consented for this long-term prospective study. The documentation of RUTI based on the current definition of 3 documented and treated UTIs in the past year or 2 in the past 6 months will be recorded. A 3 day diary with recordings of urine pH before each meal and before bed will be obtained to document that the patient has consistent low urine pH (<6), a critical condition for methenamine conversion to formaldehyde. Then the patient will be asked to take a tablet of Hiprex 1gm and to provide one subsequent urine samples at 1 hour after the intake of Hiprex. These midstream urine samples will be processed and transferred to our Lab on campus (K2 building) before being sent to our partnering lab at UTD run by [name] for testing, including urine pH testing, and the measurements of methenamine and aldehyde produced in these urine samples.

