#### Part 2:

Patients already on a methenamine drug will be queried on the history of their exposure (duration of intake, effect on RUTI, current urine pHs, etc). Patients will provide a urine sample. If the urine culture is negative, the patient will begin their prescription of Hiprex by manufacturer recommendations (if not already doing so). If the urine culture returns positive, they will be treated with a course of culture-based antibiotics and will begin Hiprex once their urine results confirm a negative culture.

Based on our preliminary data on seven women followed for one year, the levels in urine (ratioed to urinary creatinine to account for urine dilution) remain fairly stable over time.

Therefore, we don't need to follow women on Hiprex as closely as we intended to at the start of this project. Now we suggest that patients return to clinic at 3 months, 6 months, and 12 months after the onset of their Hiprex treatment to provide urine samples. During these follow-up visits, patients will also fill out a standardized, validated questionnaire regarding UTI symptoms. Data concerning common Hiprex side-effects and compliance with self-administration of Hiprex will also be collected. Hiprex will be stopped when clinically indicated based on the onset of such side-effects. Urine acidity and concentration of methenamine and formaldehyde will be analyzed in these urine samples. Hiprex dosage will be increased if concentration of formaldehyde is not above the threshold for bacteriostatic effects.

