## **10. Potential Risks:**

- a. To the participants who were already taking Hiprex, there are no direct risks because this study would not change their routines.
- b. To the participants who were not initially taking Hiprex, risks include any adverse side effects associated with the medication; however, patients will be monitored very closely after the start on Hiprex therapy.
- c. Tracked information will be used from patient records (EMR in EPIC), and identifiable information will be removed prior to analysis to ensure anonymity. Thus, all possible efforts will be made to protect patient confidentiality. Potential breach of PHI will be minimized with use of encrypted data devices stored in locked and protected areas.

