## **13. Potential Benefits:**

- a. To the participants who were already taking Hiprex, there are direct benefits because this study will confirm that they are either taking Hiprex with adequate urinary dosing or need adjustments in Hiprex dose and/or urine pH to improve Hiprex efficacy.
- b. To the participants who were not initially taking Hiprex, benefits would include a possible reduction in the frequency and severity of RUTIs over time if Hiprex is shown to be metabolized in their urine to produce adequate formaldehyde levels.
- c. To the individuals not involved in this study, the study will provide directions for future randomized control trials involving Hiprex and another comparator.

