## 14. Biostatistics:

Since this is a pilot study, our goal is to enroll 100 patients with RUTIs willing to be closely monitored for 1 year on Hiprex once the appropriate dosing has been confirmed. The acquired data will inform power calculations for a future randomized control trial.

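### The dose-adjustment rule appears in two incompatible forms and Part 1 does not establish a dose, so the one-year UTI count is not a count at confirmed dosing; the risk statement for current users also conflicts with the procedures

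*Combined protocol and SAP*

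**What the plan says.** **Adjustment rule.** Section 3 (Part 2): "Hiprex dosage will be increased if concentration of formaldehyde is not above the threshold for bacteriostatic effects". Section 4 (Follow-up): if methenamine/formaldehyde is inadequate for bacteriostatic or bactericidal activity, "the dosage might be increased to 1.5 PO BID, and/or diet-adjustment might be considered to decrease urine pH".

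**When dosing is settled.** Section 3 (Study Design) describes Part 2 as a long-term assessment "with Hiprex taken at a proper dosing (as established in Part 1"). Section 14 describes a year of monitoring on Hiprex "once the appropriate dosing has been confirmed". The Part 1 procedure is a 3-day pH diary, one 1 g tablet and one urine sample an hour later.

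**How Part 2 starts.** Section 3 (Part 2) starts women on the manufacturer's recommendation. Section 4 (Initial visit) says: "Patients will be prescribed Hiprex 1 g PO BID for 3 months with 4 refills (total of 1 year"). Visits are timed at 3, 6 and 12 months from the start of Hiprex. The primary outcome counts UTI events over the one-year study period and does not mention dose changes.

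**Risk to current users.** Section 10(a): "there are no direct risks because this study would not change their routines". Section 13(a) lists as a benefit to the same women that they may learn they "need adjustments in Hiprex dose and/or urine pH to improve Hiprex efficacy".

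**The concern.** There are three problems, and they bear on what the trial's main number will mean.

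First, two sections give the same rule differently. Two clinicians holding the same urine result could act differently, and both would be following the protocol. Exposure would then depend on which section was read.

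Second, the plan presents its result as the effect of Hiprex once each woman's dose has been confirmed, and intends to use that result to power a randomised trial. If no step confirms the dose before counting starts, the rate carried forward describes something else: a standard starting prescription, changed for some women part-way through.

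Third, the no-risk statement for current users rests on a premise that the procedures contradict. Anyone assessing risk from Section 10 alone would not learn that the study can alter these women's dose, diet or dose timing.

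**Working it through.** **1. The two forms of the rule**

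| Element | Section 3, Part 2 | Section 4, Follow-up |
|---|---|---|
| Obligation | mandatory | optional |
| Analyte | formaldehyde | methenamine/formaldehyde |
| Standard | bacteriostatic | bacteriostatic or bactericidal |
| Numeric threshold | none | none |
| New dose | not given | 1.5, no unit |
| Alternative | none | diet change, with or instead of a dose change |

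A bacteriostatic figure of 25 µg/mL appears in Section 2, but only as a finding from the literature; neither rule adopts it.

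Take a woman with low formaldehyde at month 3. Under the mandatory form she spends up to 12 − 3 = 9 months of the year on an increased dose. Under the optional form it can be anything from 0 to 9 months.

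**2. Does Part 1 settle the dose?** Its stated aim is the best dose for each patient. It tests one dose level, takes one post-dose sample, and has no rule turning the result into a dose. Part 2 then starts at the standard prescription whatever Part 1 shows. The only described adjustment is at the follow-up visits. No procedure implements Section 14's order of confirming the dose first and then monitoring for a year.

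**3. How much of the year is affected.** Assume the counted year starts with Hiprex in the study and that adjustment happens at a scheduled visit.

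- Change at month 3: 3/12 = 25% of the year before adjustment.
- Change at month 6: 6/12 = 50%.
- Change at month 12: 12/12 = 100%; the change affects none of the counted year.

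These fractions apply only to women whose dose is changed. Call their share *f*. The documents do not give it, so 10% to 50% is my assumption. Ignoring dropout, adjusted-dose person-time as a fraction of the cohort's year is:

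- all changes at month 3: *f* × 9/12, from 0.10 × 0.75 = 7.5% to 0.50 × 0.75 = 37.5%;
- all changes at month 6: *f* × 6/12, from 0.10 × 0.50 = 5% to 0.50 × 0.50 = 25%.

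**4. Risk statement.** Section 10(a) says routines do not change. Section 3 (Part 2) provides for dose increases. Section 4 (Follow-up) provides for a dose increase, a diet change, and holding back the first dose on visit days. Section 13(a) counts adjustment as a benefit to current users. Section 10(a)'s reason for finding no direct risk cannot stand beside these.

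**5. Supply (minor).** The plan's figure is 12 months. As written, an initial 3-month fill plus four refills is 3 + 4 × 3 = 15 months. Twelve months follows only from four fills in all: 3 + 3 × 3 = 12.

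**The case against.** The strongest defence is that counting UTIs from the start of a titrated regimen is a coherent strategy, especially in a pilot. The mixing matters only if doses change, and Section 3 reports fairly stable urinary levels over a year in seven women. A woman adequate at the starting dose has no unadjusted time. One first found inadequate at month 6 may have been adequate at month 3, so 50% before adjustment is not 50% at a wrong dose. The missing unit can be guessed from the starting prescription. All of this is fair, and it limits the size of the problem. It does not make the two rules agree or give Part 1 a decision step. If the titrated regimen is what is being studied, the plan should say so.

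A reader might go further in several ways that the documents do not support:

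- **That a 1-hour sample is too early because Section 2 cites 3 hours.** That figure is ex vivo, for bactericidal levels at pH 6.0. Section 2 also reports hydrolysis 20 times faster at pH 5.0 (180/20 = 9 minutes by that ratio). The diary is meant to document pH below 6.
- **That Part 1 repeats the design Section 2 criticises,** where "the urine samples were only taken after the first dose of Hiprex rather than after several days or months of Hiprex intake". Part 1 also takes women already on the drug, and the study samples again at 3, 6 and 12 months.
- **That participants are misinformed at consent.** The consent and information texts are not available for review. The demonstrable conflict is within the protocol.
- **That a quarter of every woman's year is at the wrong dose.** The fraction applies only to women whose dose changes.

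**Conclusion.** The point holds as an internal contradiction that should be corrected before the results are described or reused. The adjustment rule differs between its two statements on obligation, analyte, standard and available action, and its only stated new dose lacks a unit. Dosing is said to be settled before the monitored year, but no described step settles it. Section 10(a)'s premise conflicts with Sections 3, 4 and 13.

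For a woman whose dose is changed, at least 25% of the counted year precedes the scheduled adjustment. The effect on the cohort rate cannot be sized, because the share of such women is not given. The calculation assumes that the year starts with Hiprex in the study and that adjustment happens at scheduled visits.

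It would be too strong to say that the trial can learn nothing about UTI rates on Hiprex. It can report UTIs from the start of a regimen that may be adjusted; it cannot label that result as efficacy at confirmed dosing. The refill discrepancy is clerical and touches no endpoint, since the outcome is fixed at one year.

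**What to change.** 1. The sponsor should reconcile Section 3 (Study Design and Part 2), Section 4 (Follow-up) and Section 14 into one adjustment rule. It should state the trigger analyte, the sample, the threshold, whether action is required or optional, and the unit. The content is a clinical decision and none is proposed here.
2. Drop or correct the claim that Part 1 establishes dosing. Describe the primary result as UTIs from the start of a regimen that may be adjusted, and carry that description into the planning of the later trial.
3. Correct Section 10(a) to say that dose, diet or dose timing may change for current users, and check that participant materials agree.
4. Record dose-change dates. The data list in Section 4 does not name them, and the spreadsheet it refers to is not shown. As a descriptive supplement only, report UTI rates before and after a dose change. State that the comparison is confounded: doses rise because levels are low, and adherence affects both levels and infections.
5. Minor: make the refill count and the stated one-year total agree in Section 4 (Initial visit).

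The cost is protocol wording, a check of participant materials, one prescription entry, and at most one added data field. No extra visits or patients are needed.
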